#### KNOCOUT BTG-001653-01

The EQ-5D-5L is a self-administered questionnaire consisting of 5 questions pertaining to specific health dimensions (mobility, self-care, pain, usually activities and anxiety and depression), and health status rating scale (visual analogue scale [VAS]). Each dimension has 5 levels: no problems, slight problems, moderate problems, severe problems, and extreme problems. If a patient has died, the last EQ-5D-5L dimension assessment prior to death will be imputed as extreme problems (coded as 5) and flagged in the listing.

The VAS records the respondent's self-rated health on a 20 cm vertical, visual analogue scale with endpoints labeled 'the best health you can imagine' (Score=100) and 'the worst health you can imagine' (Score = 0). This information can be used as a quantitative measure of health as judged by the individual respondents. If a patient has died, the last EQ-5D-5L VAS assessment prior to death will be imputed as 0 and flagged in the listing.

Each one digit number expressing the level selected for each dimension can be combined into a 5digit number describing the respondent's health state. For example, the number 11111 represents the respondent not having any problems in all five dimensions. These 5-digit numbers are health states which can be converted to an index value, where 1 represents full health and 0 is equivalent to death. A health state could be considered worse than death and the index values for those states will be less than 0. The index value will be calculated as:

Index value =  $1 - 0.9675 * (Dimension \ 1 \ Estimate + Dimension \ 2 \ Estimate + Dimension \ 3 \ Estimate + Dimension \ 4 \ Estimate + Dimension \ 5 \ Estimate)$ 

Each dimension estimate is based on the levels chosen for each dimension and can be found in appendix section 3.1.

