### 4.1 Pulmonary Embolism (PE)

---

Venous thromboembolism (VTE), comprised of deep vein thrombosis (DVT) and pulmonary embolism (PE), is the third most common cardiovascular disorder in the United States after myocardial infarction and stroke. The 2008 United States Surgeon General's Call to Action to Prevent DVT and PE estimates that 100,000 to 180,000 deaths occur annually from PE in the U.S. alone. In the 2003 U.S. Healthcare Cost and Utilization Project Nationwide Inpatient Sample database, 196,134 VTE-related events, including symptomatic DVT, symptomatic PE, and VTE-related deaths, were calculated to have occurred among acutely ill hospitalized Medical Service subjects, afflicting two out of every 100 of these subjects.

The mortality rate for acute PE exceeds 15% in the first three months after diagnosis, surpassing that of myocardial infarction. In nearly 25% of all subjects presenting with acute PE, the initial presentation is sudden death. The majority of deaths from acute PE results from right ventricular (RV) pressure overload and subsequent RV failure. Survivors of acute PE are at-risk for developing debilitating chronic thromboembolic pulmonary hypertension (CTEPH). Subjects with CTEPH typically experience a "honeymoon" period after acute PE, during which symptoms are absent despite the onset of pulmonary hypertension. Unfortunately, the condition is usually detected when pulmonary hypertension has worsened to the point that it causes dyspnea, hypoxemia, and RV failure.

Therapeutic anticoagulation with immediate parenteral anticoagulants followed by oral agents is the cornerstone of therapy for acute PE. However, while the majority of acute PE subjects has a benign clinical course with standard therapeutic anticoagulation alone, subjects with massive and submassive PE remain at increased risk for adverse clinical events, including RV failure and hemodynamic collapse.

Advanced therapy for patients with acute PE is usually reserved for patients with either massive or submassive PE. Options for advanced therapy include peripherally-administered systemic fibrinolysis, surgical pulmonary embolectomy, catheter-assisted embolectomy, and inferior vena cava (IVC) filter insertion.

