### 6.2.2 Exclusion Criteria

---

Retrospective cases must not meet the following exclusion criteria:

11. Enrollment into the OPTALYSE PE study

Prospective subjects must not meet any of the following exclusion criteria:

12. Clinician deems the subject high-risk for catastrophic bleeding
13. Life expectancy  $<$  one year

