#### 2.6 Additional outcome measures

Analyses of additional outcome measures will be performed for both the SP and EP populations. In addition to the analyses described below, additional outcome measures will also be summarized by the subgroups described in section 2.2.1. All observed data will be summarized without imputation for missing values.

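### SAP 2.6.2: as written, the EQ-5D-5L death rule overwrites surveys completed while alive and gives deaths an index of -0.281 against the SAP's own 0; QoL change from baseline has no scheduled pre-APT survey

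*SAP*

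**What the plan says.** **Death rule.** SAP 2.6.2 has two sentences on deaths in the EQ-5D-5L. For the dimensions: "If a patient has died, the last EQ-5D-5L dimension assessment prior to death will be imputed as extreme problems (coded as 5"), with a flag in the listing. For the visual analogue scale: "If a patient has died, the last EQ-5D-5L VAS assessment prior to death will be imputed as 0 and flagged in the listing". The same section describes an index scale "where 1 represents full health and 0 is equivalent to death", allows negative values for states worse than death, and computes the index from the five coded levels by formula. It gives no separate index value for a death. For the coefficients it says: "Each dimension estimate is based on the levels chosen for each dimension and can be found in appendix section 3.1"; they are in fact in appendix 3.2. SAP 2.6 sets the general rule for these outcomes: "All observed data will be summarized without imputation for missing values". It adds that "additional outcome measures will also be summarized by the subgroups described in section 2.2.1", which include the thrombolytic dose bands.

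**Baseline.** SAP 2.1 defines baseline as the last available value before APT starts, and gives QoL windows only for months 3 and 12. SAP 2.6.2 and Protocol 13.8 both plan QoL change from baseline and shift tables. The assessment schedules (Protocol section 3, SAP 1.1.1) leave the QoL cell at Baseline empty and first mark it under Day 0 to discharge. Protocol 10.1 and 10.2 list no QoL survey. Protocol 10.3 lists both instruments among items recorded once the procedure is over. Outcome 9 in Protocol 5.3 includes a baseline measurement; outcome 9 in the synopsis does not.

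**The concern.** An assessment made before death is one the patient completed. A programmer who follows the text would replace real answers with the worst possible ones, at a visit where nothing was missing. For a death before the month-3 survey, the overwritten survey is the in-hospital one; for most later deaths it is month 3. A visit's QoL summary would then depend on who dies afterwards. A dose group with more later deaths would look worse at month 3 through answers its patients did not give, and the registry's second objective is to describe how varied APT protocols affect long-term outcomes. For early deaths the in-hospital mean drops, so visit means can seem to improve by month 3 with no true change.

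If visits after death were meant, the text does not say so, and the index would still sit below the SAP's own value for death. PEmb-QOL has no death rule at all, so the two instruments would treat the same death differently.

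On baseline, the planned tables would either be empty or present a post-treatment value under the label baseline.

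**Working it through.** 1. **Reproduce the SAP's example (appendix 3.2).** State 23245: 0.051 + 0.076 + 0.051 + 0.276 + 0.301 = 0.755, and 1 - 0.9675 × 0.755 = 0.2695. The SAP prints 0.270, so the formula and table are being read correctly.

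2. **Index produced by the death rule.** Level-5 estimates from the same table: 0.275 + 0.217 + 0.190 + 0.341 + 0.301 = 1.324. Then 1 - 0.9675 × 1.324 = -0.281. The SAP's anchor for death is 0. The conflict arises on either reading, because both pass level 5 through the formula.

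3. **Literal reading, fall in a visit mean.** Let p be the fraction of a visit's respondents who die before their next survey, and t the mean index those patients actually reported. Then fall = p × (t + 0.281). Both p and t are assumptions; 0.27 is the SAP's example state rounded.

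| t | t + 0.281 | Fall at p = 5% | Gap between groups, p = 2% v 10% |
|---|---|---|---|
| 0.27 | 0.551 | 0.028 | 0.044 |
| 0.50 | 0.781 | 0.039 | 0.062 |
| 0.60 | 0.881 | 0.044 | 0.070 |
| 0.80 | 1.081 | 0.054 | 0.086 |
| 0.90 | 1.181 | 0.059 | 0.094 |

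   The last column is (0.10 - 0.02) × (t + 0.281). It supposes two dose groups with no true difference. For the VAS the fall is p × the true VAS; with an assumed 75 and p = 5% that is 3.75 points.

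4. **Apparent improvement from early deaths.** With p = 5%, t = 0.60 and survivors also at 0.60, the in-hospital mean reads 0.600 - 0.044 = 0.556. Month 3 then reads 0.600, a rise of 0.044 with no true change. A paired change is not affected by these deaths, since those patients have no month-3 survey.

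5. **Other reading (level 5 entered at visits after death).** This is an alternative to step 3, not an addition. A mean that includes deaths is too low by 0.281 × the death fraction: 0.006, 0.014, 0.028 or 0.042 at 2, 5, 10 or 15% deaths.

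6. **Baseline.** Pre-APT QoL surveys scheduled: none. The Day 0 to discharge cell could, on its own, admit a survey on Day 0 before the procedure, but Protocol 10.3 places it afterwards. SAP 2.1 has no window or selection rule for that in-hospital survey.

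**The case against.** The rule evidently aims to make deaths count, and that is a fair aim: means of completed surveys describe survivors only. Read as applying to visits after death, it can be taken as a deliberate, flagged exception to the no-imputation rule. A smaller repair would name the visit and state the index for death. QoL is outcome 9 of 10, descriptive and prospective-only; the only test named in the protocol's statistical section is Fisher's exact test on the frequency of treatment protocols. Collected answers remain in the listings under SAP 2.1.

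The limited impact stands, and so does the survivor problem, which the fix must address. But flags and listings do not correct a summary table, and the text as it stands does not express the intention. Coding level 5 would also still put unreported answers into the dimension counts and shift tables.

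Three stronger readings are tempting and are not supported:

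- A reader might infer that deaths have no specified index if the rule was meant for visits after death. The formula does supply one, -0.281, and negative values are legitimate for living respondents. The fault is the unresolved clash with 0.
- A reader might infer that month-12 answers are overwritten too. Protocol 6.3 ends participation when the 12-month follow-up is completed, and nothing shows that a death after that survey would be captured.
- A reader might take p from Protocol 4.1: "The mortality rate for acute PE exceeds 15% in the first three months after diagnosis". That is a general acute-PE figure. The registry excludes some high-risk patients (for example "Clinician deems the subject high-risk for catastrophic bleeding") but enrols massive and submassive PE, which the same section describes as at increased risk. A patient who dies before the first survey also has nothing to overwrite. The figure is neither an estimate of p nor a bound on it.

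**Conclusion.** Both parts hold and should be corrected before analysis. As written, the death rule alters observed EQ-5D-5L answers, leaves visits after death without a value, and yields an index 0.281 below the SAP's own value for death without saying which applies. The -0.281 follows from the SAP alone. The effect on a visit mean (0.028 to 0.059 at 5% later deaths) and on a dose-group contrast (0.044 to 0.094 for 2% v 10%) is illustration only: it rests on assumed death fractions and assumed pre-death indices of 0.27 to 0.90.

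The QoL baseline is a contradiction within the documents: an analysis and one version of the outcome call for a measurement that the schedule does not contain. Neither part affects a hypothesis test. The consequence is misleading QoL tables in a descriptive, prospective-only outcome.

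**What to change.** **Deaths.** Delete both overwrite sentences (dimensions and VAS). Summarise each completed survey as observed at its own visit, and show beside it the number of prospective patients who had died by that visit, from the death data already summarised under SAP 2.7.2. If deaths are to be scored, do it in a supplementary summary, only at scheduled visits after death, with index = 0, VAS = 0 and no imputed dimension levels.

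**Baseline.** For QoL only, name the post-procedure-to-discharge survey as the reference and add a window and selection rule for it to SAP 2.1. Label the results *change from post-procedure*, and state that they cannot show improvement from the pre-treatment state. Record this as a known difference from Protocol 5.3, and reconcile 5.3, the synopsis and the schedule at the next amendment.

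**Clerical.** Change the appendix pointer from 3.1 to 3.2.

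**Cost.** SAP wording, table titles and one death-count row per QoL table; no new data. The protocol change needs approval by the investigator, sponsor and IRB/EC (Protocol 15.7), so it can travel with the next amendment. Until then the SAP openly differs from Protocol 5.3. Observed-only later means describe survivors, which is why the death counts belong beside them.

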# 2.6.3 Adjunctive Therapy

The number and percentage of patients with non or partial response to other interventional procedures prior to APT procedure for index PE (eg, patients receiving other procedures prior to EKOS for their index PE) will be summarized using descriptive statistics.

The number and percentage of patients who receive adjunctive treatment following treatment with EKOS for their index PE will be summarized using descriptive statistics.

# 2.6.4 IVC Filter Placement

The number of occurrence of IVC filter placement will be summarized using descriptive statistics.

# 2.7 Safety analyses

Safety analyses will be performed for the SP during hospitalization and through the 12-month follow-up period. In addition to the analyses described below, safety analyses will also be summarized by the subgroups described in section 2.2.1.

#### 2.7.1 Adverse events

# 2.7.1.1 Coding

Adverse events will be coded according to Medical Dictionary for Regulatory Activities (MedDRA) version 20.1.

## 2.7.1.2 General

Adverse event summaries will include all treatment emergent adverse events (TEAE). TEAE are defined as AEs starting on or after study day 1 (i.e., on or after the first day of APT treatment). All adverse events will be listed and non-TEAEs will be flagged.

TEAEs will be summarized by presenting the number and percentage of patients having at least one TEAE, having at least one TEAE in each primary system organ class (SOC) and for each preferred term (PT). A patient with multiple occurrences of a TEAE will be counted only once in the category.

Separate summaries will be presented by SOC and PT.

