### 4.3 EKOS Clinical Summary in Pulmonary Embolism

ULTIMA, SEATTLE II, and OPTALYSE PE have shown various APT regimens using recombinant tissue plasminogen activator (r-tPA) for thrombolysis to be safe and effective in the treatment of PE. Low dose r-tPA and reduction in treatment time of the APT procedure appear to reduce bleeding events and costs associated with length of stay in the ICU and hospital.

Pharmacology studies demonstrate that clot lysis occurs rapidly after r-tPA intravenous treatment and is  $\sim 90\%$  complete by 90 minutes. A rabbit study demonstrated that thrombolytic activity after r-tPA, whether administered as an intravenous bolus dose or infusion is dose-dependent and the duration of action is dose-independent. After a single dose (0.5 to 0.4 mg/kg), to 2.3-3 kg rabbits, r-tPA was rapidly inhibited, resulting in duration of action of 15 minutes. The maximum extent of lysis after the bolus was 54% for a 0.4 mg/kg dose. During a 4 hour infusion of r-tPA (0.625 to 1 mg/kg), 90% of the thrombolytic activity occurred within 2 hours. The maximum extent of lysis after the infusion was 87% for a 0.5 mg/kg dose. After administration of either a bolus or infusion, continued lysis activity decreased exponentially with time and there remained an undissolved clot at the end of the measurement period

Similarly, a pharmacodynamics study of r-tPA in man demonstrated that even though the initial half-life of r-tPA in the systemic circulation is 3-4 minutes, fibrinolysis after an intravenous infusion of 20 to 150 mg continues from 7 to 12 hours. The prolonged duration of action demonstrates that plasmin bound to fibrin continues to be active after r-tPA is cleared from the circulation. As fibrin is lysed, r-tPA is released and is metabolized by the liver.

The ability of r-tPA to lyse clot is dependent upon binding with fibrin and plasminogen in a centric ternary complex to activate plasminogen to form plasmin which lyse fibrin into degradation products. Clot lysis is diffusion dependent. By increasing permeation, lysis increases. Several in-vitro studies have demonstrated that ultrasound enhances both urokinase and r-tPA mediated lysis of plasmin and blood clots. Enhancement is seen at a range of frequencies, intensities and lytic concentrations. This enhancement is seen in both static and flowing thrombolytic models. Animal studies report faster recanalization times for clots exposed

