### **9.1.4 Adjunctive Interventions**

---

Investigator may utilize any adjunctive interventions as deemed necessary according to their clinical judgement. Investigator will note any adjunctive interventions to the APT procedure for the treatment of PE including type, start date, and stop date in the EDC system.

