# 2.2 **Populations**

Safety Population (SP) - The SP will be defined as all patients who receive the APT procedure. Safety and effectiveness summaries will be reported for the SP.

Efficacy Population (EP) - The EP will be defined as all patients who meet eligibility criteria. An additional effectiveness summary will be reported for the EP.

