# 2.2.1 Subgroups

Efficacy and safety outcome measures will be summarized separately for the following subgroups:

- APT dose received (ie, >24mg; 20.1-24mg; 12.1-20mg; 4-12mg; <4mg)
- Submassive and massive PE

- Region
- Retrospective and prospective portions of the registry

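### The dose-band tables do not separate patients who had another reperfusion treatment before or after APT, and the day-level TEAE rule admits same-day events that precede APT

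*SAP*

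**What the plan says.** The plan expects a second treatment in some patients. Protocol 5.3 makes adjunctive therapy after APT an outcome (number 3, frequency and safety), and likewise inadequate response to other procedures before APT (number 4). Protocol 9.1.4 sets no limit: "Investigator may utilize any adjunctive interventions as deemed necessary according to their clinical judgement". SAP 2.6.3 reports a number and percentage for the earlier group ("patients receiving other procedures prior to EKOS for their index PE") and for patients with adjunctive treatment afterwards. The opening of SAP 2.6 extends these counts to the subgroups.

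Neither analysis population removes these patients. In SAP 2.2, "The SP will be defined as all patients who receive the APT procedure" and "The EP will be defined as all patients who meet eligibility criteria". Other reperfusion is not an eligibility criterion; the only retrospective exclusion is "Enrollment into the OPTALYSE PE study".

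The first subgroup in SAP 2.2.1 is "APT dose received (ie, >24mg; 20.1-24mg; 12.1-20mg; 4-12mg; <4mg". The others are PE severity, region and registry portion. Efficacy (SAP 2.5) and safety (SAP 2.7) are both to be summarised by these subgroups.

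Baseline is the latest value before APT (SAP 2.1), and the post-treatment RV/LV image falls 24 to 48 hours after APT starts (Protocol 5.3). For adverse events, SAP 2.7.1.2 states: "TEAE are defined as AEs starting on or after study day 1 (i.e., on or after the first day of APT treatment".

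**The concern.** The second objective is to describe the effects of different APT protocols on outcomes. The dose-band tables are where a reader will look for that. If some patients in a band also had embolectomy or systemic lysis, the band's RV/LV change and bleeding rate describe a mixture of treatments. An intervention added before the 24 to 48 hour image can change RV/LV, and the result is reported under the APT dose. A treatment given before APT can still be acting when APT starts. Adjustment for baseline severity would not remove this, because the contamination is a second treatment and not a patient characteristic.

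The TEAE rule raises a smaller question of the same kind. It works by calendar day, so it cannot tell a bleed that preceded APT on the procedure day from one that followed it.

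**Working it through.** The plan states no power, error rate or effect size that depends on this point, and its sample size is a feasibility count. There is no figure to reproduce. The check is a trace through the documents, then an illustration.

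**1. Trace.** Both groups are in the Safety Population. Both are in the Efficacy Population if eligible. No subgroup separates them. No rule in SAP 2.1 or 2.5 deals with an intervention between APT and the image, or with a baseline image taken before an earlier treatment. The counts in SAP 2.6.3, read with SAP 2.6, will show how many such patients each band holds, but not what their outcomes were.

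**2. RV/LV illustration.** Protocol 4.3 gives OPTALYSE PE changes at 48 hours of -0.22, -0.25, -0.18 and -0.32. The six pairwise gaps are 0.03, 0.04, 0.07, 0.07, 0.10 and 0.14. If the extra effect is the same in each band:

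spurious difference between two bands = (difference in share with other reperfusion) × (extra RV/LV change from it)

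Both inputs are assumptions.

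| Difference in share | Extra 0.10 | Extra 0.20 | Extra 0.30 |
|---|---|---|---|
| 5 points | 0.005 | 0.010 | 0.015 |
| 10 points | 0.01 | 0.02 | 0.03 |
| 20 points | 0.02 | 0.04 | 0.06 |
| 30 points | 0.03 | 0.06 | 0.09 |

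Imbalances of about 10 to 20 points can reach the smaller gaps. With equal shares and equal effects the difference is zero, although each band's level is still shifted. If co-treated patients improve less than others, as non-responders may, the sign reverses.

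**3. Bleeding illustration.** Band rate = (1 - f) × base + f × co-treated rate, with an assumed base of 3% and an assumed 6% to 20% in co-treated patients:

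- f = 5%: 2.85% + 0.30% to 1.00% = 3.15% to 3.85%
- f = 10%: 2.70% + 0.60% to 2.00% = 3.3% to 4.7%
- f = 20%: 2.40% + 1.20% to 4.00% = 3.6% to 6.4%

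Whether major bleeding will be tabulated by band is itself unclear. SAP 2.2.1 and 2.7 say that safety is summarised by subgroup, but the list of four subgroup tables closing SAP 2.7.1.3 omits the bleeding items. Bleeding terms would still appear by band in the table of all adverse events.

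**4. TEAE rule.** Retrospective events are collected under post-procedure and long-term data (Protocol 8.3, 8.4). The prospective schedule starts event collection in the procedure column. Protocol 12.1.1 counts an adverse event only from enrollment. What remains is mainly a prospective event after enrollment, on the procedure day, before APT. SAP 3.1.1 adds a related case: an incomplete start date in the treatment month or year is set to the treatment date, which makes the event treatment-emergent.

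**5. Dose.** SAP 2.2.1 refers to APT dose, whereas SAP 2.4.1 categorises by thrombolytic dose without saying whether a non-catheter dose counts. The two need not put a patient with systemic lysis in the same band.

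**The case against.** Keeping every patient under the APT regimen received is a legitimate treatment-policy description for a standard-of-care registry. That stands, and the all-patient tables should remain the main result. Regimen outcomes are descriptive with confidence intervals and no test between regimens, so no error rate is at stake. Related-event tables, investigator attribution to thrombolytic and anticoagulant (Protocol 12.2) and full listings also help. None of them splits a band's results, and the attribution fields include no other reperfusion procedure.

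A reader might infer three stronger points that the documents do not support.

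- **Low doses will look more effective and less safe than they are.** This needs more co-treated patients in the low bands. Nothing in either document says so.
- **Earlier lysis carries bleeding risk into the bands.** The protocol says that "fibrinolysis after an intravenous infusion of 20 to 150 mg continues from 7 to 12 hours", but this describes clot lysis, not bleeding. Outcome 4 concerns interventional procedures, leaves the term undefined and does not name systemic lysis. A baseline image repeated after the earlier treatment would also absorb the gain already made. Prospective patients judged at high risk of catastrophic bleeding are excluded.
- **Regimens should be compared only in patients with APT alone.** For added treatment, this selects on something that happens after APT starts and may reflect failure of the regimen. It could flatter the regimens that fail most often.

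**Conclusion.** The gap is real but modest. The plan identifies patients with a second treatment, counts them, and then leaves them unseparated in the dose-band outcome tables. The size and direction of any bias are unknown: every share and effect used above is assumed, and a difference between bands is distorted only if shares or effects differ by band. The illustration shows only that plausible imbalances could match the smaller regimen gaps quoted in the protocol. The TEAE weakness is real but confined mainly to a short prospective interval. Both affect how the second objective can be read, not the validity of a test. This is a low-cost improvement to the SAP, not a fault that undermines the registry.

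**What to change.** 1. Keep the all-patient dose-band tables as the main description.
2. Add a supplementary dose-band table of RV/LV change and major bleeding, split by reperfusion treatment before APT (yes, no, unknown). State which treatments count. Use the data already needed for outcome 4. This is a characteristic fixed before APT, so the split does not select on the result of APT.
3. Within the subgroup counts that SAP 2.6 already foresees, show added reperfusion by dose band. Flag RV/LV images taken after it and present RV/LV change with and without those images. Do not base the regimen comparison on patients free of added treatment.
4. Define TEAEs as events starting at or after the APT start time where the time is known, and keep the day rule otherwise.
5. State in SAP 2.4.1 whether thrombolytic dose includes non-catheter doses, and align it with SAP 2.2.1.

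Cost: mainly SAP wording, flags and a few tables, some with small cells. Capture is the limit. Protocol 9.1.4 records adjunctive start and stop dates without times, and only in the prospective section. The retrospective lists in Protocol 8 do not name earlier or added reperfusion, and Protocol 11.7 restricts which non-anticoagulant drugs are recorded. Same-day order and many retrospective cases may be unclassifiable and should be shown as unknown. Any new data item needs a protocol amendment with the approvals in Protocol 15.7.
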